9.1.2 Adverse Events in the Single-blind Placebo Run-in Period

Adverse Events in the single-blind placebo run-in period will be summarized for patients in the Safety Sample. AEs occurring up to 30 days after the last day of IMP in this period, but prior to the start of the double-blind treatment period, will be included in these summary tables. The incidence of adverse events in the single-blind placebo run-in period will be tabulated by the double-blind treatment patients receive in the double-blind treatment period.

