3.7.1.2 Visit 2 (Single-blind Placebo Run-in)

After the subject has completed the medication washout period (if applicable), the Visit 2 (Day -7) assessments described in the Schedule of Assessments (Table 3.7-1) will be performed. The following should also be noted:

- Urine drug screen results from the previous visit will be reviewed. If the subject is positive for any prohibited medications at screening (including medications for the treatment of ADHD, see Section 4.1), and has not had a negative repeat urine drug screen confirmed since, the subject will be screen failed.
- Subjects will be administered the ASRS prior to the start of the single-blind placebo run-in period, and those with a $\geq 30\%$ improvement in the (18-item) ADHD Symptoms score compared to the score at screening will be screen failed, and not eligible for rescreening.
- All subjects must be unaware of the single-blind placebo run-in period so that it is indistinguishable from the double-blind treatment period. All subjects must be under the impression that they are starting to receive randomized treatment at the time of Visit 2 (Day -7).
- Placebo will be dispensed for the single-blind placebo run-in period, and subjects will be instructed to take their first dose from the dosing card in the clinic. Subjects will be instructed to take their doses at approximately the same time every day.
- The subject will download the AiCure Platform (Section 3.12) or receive a provisioned device with the AiCure Platform predownloaded, and will be trained on IMP compliance using this application.
- Subjects who discontinue the trial during the single-blind placebo run-in period should be considered early termination subjects, and should proceed with the early termination visit (Section 3.7.1.4.2) and follow-up procedures (Section 3.7.1.5 and Section 3.7.1.6).

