3.9 Screen Failures

A screen failure subject is one from whom informed consent is obtained and is documented in writing (ie, subject signs an eICF), but who is not randomized or assigned to trial treatment.

For this trial, treatment begins with the first dose of the IMP in the single-blind placebo run-in period. Subjects that have a positive alcohol test (via breathalyzer or blood), or positive drug screen for cocaine, or other illicit drugs (excluding marijuana) are not eligible to be retested or rescreened, and will be considered screen failures. Subjects that test positive for marijuana may be permitted to be enrolled if they have no evidence of a substance use disorder, and if they agree to refrain from use for the duration of the trial. Allowance for subjects testing positive for marijuana at screening require explicit approval from the medical monitor. Subjects that test positive for confirmed prescription use of ADHD medications at screening will be required to undergo a washout period (Section 4.1). If after the allotted washout period, a subject tests positive for ADHD medications prior to the start of the single blind placebo run-in period, subjects will be screen failed, and not permitted to rescreen. Screen failures previously excluded for a positive urine drug screen due to use of prescription or over-the-counter (OTC) medications or products not used for the treatment of ADHD, may be retested or rescreened for participation in the trial only with the explicit consent of the medical monitor. Subjects will be administered the ASRS prior to the start of the single-blind placebo run-in period, and those with a $\geq 30\%$ improvement in the (18-item) ADHD Symptoms score compared to the score at screening will be screen failed, and not eligible for rescreening. Screen failures excluded for any other reasons may be rescreened at any time if the exclusion characteristic has changed. In the event that a screen failure is rescreened a new eICF must be signed, a new screening number assigned, and all screening procedures repeated.

Protocol 405-201-00014

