5.1 Data Sets for Analysis

The following analysis samples are defined for this trial:

Enrolled Sample: comprises all subjects who signed an informed consent form (ICF) for the trial and enrolled into the single-blind placebo run-in period.

Randomized Sample: comprises all subjects who were randomized in the double-blind treatment period. Subjects are considered randomized when they are assigned a treatment group by eSource at the end of single-blind placebo run-in period. A subject receiving IMP outside of the eSource will not be considered randomized, but safety will be reported.

Safety Sample: comprises those randomized subjects in the double-blind treatment period who received at least one dose of double-blind IMP as indicated on the dosing record.

Subjects will only be excluded from this population if there is documented evidence (i.e., drug

SAP 405-201-00014

dispensed = drug returned or no IMP dispensed) that the subject did not take IMP. If a subject is dispensed IMP and is lost to follow up, he/she will be considered exposed.

Efficacy Sample: the Full Analysis Set (FAS) comprises all subjects in the Safety Sample who have a baseline value and at least one valid post-randomization efficacy evaluation for AISRS total score in the double-blind treatment period.

Per Protocol (PP) Sample: comprises those subjects in the Efficacy Sample who complete at least the first 2 weeks of double-blind medication ((last day of IMP - first day of IMP + 1) \geq 14 days) and have at least one post baseline AISRS measurement on or after Day 14 visit during the double-blind treatment period without major protocol violations deemed to compromise the assessment of efficacy. These major protocol violations will be any of the followings:

1. Subjects who were not at least 80% or were more than 120% compliant with double-blind IMP or missed 7 or more consecutive days of dosing immediately prior to the Day 42/ET AISRS measurement date during the double-blind treatment period based on subject-reported (eCRF) compliance data
2. Subjects who reported concomitant medication use that will impact the primary efficacy endpoint
3. Subjects who had major protocol deviation as represented on the protocol deviation eCRF page that will impact the primary efficacy endpoint
4. Subjects who took the wrong study treatment

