8.5 Exploratory Analysis

Exploratory efficacy analyses will be presented in Statistical Documentation.

Treatment-by-center interaction will be assessed at Day 42 by including the treatment-by-center-by-visit interaction in the model. Results for study centers will be displayed from largest center to smallest center.

Line Item score will be performed for AISRS and ASRS on Change from baseline of the double-blind treatment period to Day 42 using the MMRM model for AISRS and ASRS, where Cohen's D Effect Size¹⁰ is the difference between the two means divided by their standard deviation [as defined by Cohen's D and reviewed on pages 4-6 from the Sage book "Effect Size for ANOVA Designs" (Vol 129) by Cortina and Nouri]. For MMRM (using SAS PROC MIXED), or ANCOVA (Using SAS PROC GLM), LSMean difference of treatment effects for the between centanafadine and placebo groups, and the standard error of the difference (Stderr) will be obtained with an Estimate statement. Let n_1 and n_2 denote the

SAP 405-201-00014

respective sample sizes of the two groups to compare, Effect Size = $d = (\text{LSMean}_1 - \text{LSMean}_2) / \sigma$, where $\sigma = \frac{\text{Stderr}}{\sqrt{\frac{1}{n_1} + \frac{1}{n_2}}}$.

9 Safety Analysis

Standard safety variables to be analyzed include AEs, clinical laboratory tests, vital signs, electrocardiograms (ECGs), body weight, waist circumference, and BMI. In addition, data from the following safety scales will be evaluated: C-SSRS and Study Medication Withdrawal Questionnaire (SMWQ).

Analyses of the double-blind treatment period safety data will be performed on the Safety Sample unless indicated otherwise.

The Safety Sample will also be analyzed for the single-blind placebo lead-in period safety data, as applicable, by treatment groups the subjects eventually being assigned in the double-blind treatment period.

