- CT-8.2.1.3 Incidence of TEAE During the Double-Blind Treatment Period of at Least 5% in Any Centanafadine Group and Greater Than Placebo by System Organ Class and MedDRA Preferred Term (Safety Sample)
- CT-8.2.1.4 Incidence of TEAEs During the Double-Blind Treatment Period by System Organ Class and MedDRA Preferred Term, by Sex (Safety Sample)
- CT-8.2.1.5 Incidence of TEAEs During the Double-Blind Treatment Period by System Organ Class and MedDRA Preferred Term, by Race (Safety Sample)
- CT-8.2.1.6 Incidence of Non-Serious TEAEs During the Double-Blind Treatment Period of at Least 5% in Any Centanafadine Group and Greater Than Placebo by System Organ Class and MedDRA Preferred Term (Safety Sample)
- CT-8.2.1.7 Incidence of TEAE During the Double-Blind Treatment Period of at Least 2% in Any Centanafadine Group and Greater Than Placebo by System Organ Class and MedDRA Preferred Term (Safety Sample)
- CT-8.2.1.8 Incidence and Occurrence (Number of Events) of Serious TEAEs by System Organ Class and MedDRA Preferred Term (Safety Sample)
- CT-8.2.1.9 Incidence and Occurrence (Number of Events) of Potentially Drug-Related Serious TEAEs by System Organ Class and MedDRA Preferred Term (Safety Sample)
- CT-8.2.1.10 Incidence and Occurrence (Number of Events) of Non-Serious TEAEs by System Organ Class and MedDRA Preferred Term (Safety Sample)
- CT-8.2.2 Incidence of AEs During the Single-Blind Placebo Run-in Period by System Organ Class and MedDRA Preferred Term (Safety Sample)
- CT-8.3.1 Incidence of Potentially Drug-Related TEAEs During the Double-Blind Treatment Period by System Organ Class and MedDRA Preferred Term (Safety Sample)
- CT-8.3.2 Incidence of Potentially Drug-Related TEAEs During the Double-Blind Treatment Period by System Organ Class, MedDRA Preferred Term and Severity (Safety Sample)
- CT-8.4.1.1 Incidence of Deaths Due to TEAEs During the Double-Blind Treatment Period by System Organ Class and MedDRA Preferred Term (Safety Sample)
- CT-8.4.1.2 Incidence of Deaths Due to TEAEs During the Double-Blind Treatment Period by System Organ Class and MedDRA Preferred Term and Severity (Safety Sample)
- CT-8.4.2 Incidence of Deaths Due to AEs During the Single-Blind Placebo Run-in Period by System Organ Class and MedDRA Preferred Term (Safety Sample)
- CT-8.5.1.1 Incidence of Serious TEAEs During the Double-Blind Treatment Period by System Organ Class and MedDRA Preferred Term (Safety Sample)

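### Run-in safety tables are restricted to subjects later randomized and dosed, so anyone who dies, stops or is early terminated before the first double-blind dose is left out of them

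*SAP*

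**What the plan says.** The opening of SAP Section 9 sets the general rule: "The Safety Sample will also be analyzed for the single-blind placebo lead-in period safety data", tabulated by the arm to which subjects are later assigned. Section 9.1.2 applies it to adverse events: "Adverse Events in the single-blind placebo run-in period will be summarized for patients in the Safety Sample". Sections 9.2.2, 9.2.3, 9.3, 9.3.2, 9.4.2 and 9.6 repeat it for liver-injury cases, laboratory tests, vital signs, ECG and C-SSRS.

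The Safety Sample, in SAP Section 5.1, "comprises those randomized subjects in the double-blind treatment period who received at least one dose of double-blind IMP as indicated on the dosing record". The same section defines a wider set: "Enrolled Sample: comprises all subjects who signed an informed consent form (ICF) for the trial and enrolled into the single-blind placebo run-in period". No safety summary uses that wider set.

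The protocol treats the run-in as part of treatment. Section 3.9 says: "For this trial, treatment begins with the first dose of the IMP in the single-blind placebo run-in period". Section 3.7.1.2 says: "Subjects who discontinue the trial during the single-blind placebo run-in period should be considered early termination subjects". Section 3.7.1.3 gives the same status to subjects who fail exclusion criteria 30 to 32 at baseline. Both groups go through the early termination visit and follow-up.

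**The concern.** A safety summary of a period should cover the people exposed in that period. Here, membership depends on what happened afterwards: a subject must get through the run-in, be randomized and take a double-blind tablet before any run-in event is counted. Subjects whose run-in ended in death or in withdrawal for an adverse event are removed from both numerator and denominator.

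At stake is whether a reader of the study report can see what happened to everyone who took run-in placebo. The protocol requires the data on early-terminated subjects to be collected, yet the planned incidence tables do not show them.

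**Working it through.** No figure in the plan needs reproducing. The check compares definitions, the visit schedule and the list of outputs.

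1. **Membership.** Inputs: the Safety Sample definition (SAP 5.1), the run-in start at Visit 2, Day -7 (Protocol 3.2.1), and randomization at Visit 3, Day -1, with double-blind dosing from the next day, Day 1 (Protocol 3.7.1.3). Safety Sample = randomized AND at least one double-blind dose. A subject who dies or stops between Day -7 and the first double-blind dose fails the second condition, and usually the first. That subject's contribution to any Safety Sample table is 0 events and 0 subjects. There is one narrow exception. SAP 5.1 removes a subject only on documented evidence that no tablet was taken, and counts as exposed someone who was dispensed drug and then lost to follow-up. A subject given a double-blind card at baseline could therefore remain in the sample.

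2. **Are the data collected?** Yes. Protocol Table 3.7-1 schedules adverse events, vital signs, laboratory tests, ECG and C-SSRS at the Day 42/ET visit, which run-in discontinuers must attend. Protocol 5.2 starts SAE collection at consent. Table 3.7-2 follows early-terminated subjects to 10 (+2) days after the last dose.

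3. **The 30-day window.** SAP 9.1.2 also admits events up to 30 days after the last run-in dose, provided double-blind treatment has not begun. Run-in dosing continues through the baseline visit, and double-blind dosing starts the next day. For a Safety Sample member the window is therefore roughly one day of the 30. It has real content mainly for subjects who do not continue, and they are the ones the sample excludes.

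4. **Outputs in SAP Section 13.**

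| Output | Population in title | Early-terminated run-in subjects shown? |
|---|---|---|
| CT-8.1.2, 8.2.2, 8.5.2.1 (run-in AEs and SAEs) | Safety Sample | No |
| CT-8.4.2 (run-in deaths) | Safety Sample | No |
| CT-10.3.x, 10.4.2, 10.5.2, 11.3.x, 12.4.x, 12.5.x, 14.2.x, 17.3, 17.4 | Safety Sample | No |
| CT-9.1.2, 9.2.2 (listings of run-in deaths and SAEs) | None stated | Unclear |
| CT-8.6.1, 8.6.2, 9.3, 9.4 (AE discontinuations) | Double-blind period only | No run-in counterpart |

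SAP 6.1 does not fill the last gap, because it summarizes discontinuation reasons only for the Randomized Sample in the double-blind period.

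5. **Size.** Protocol 3.3.1 plans up to 1150 screened and about 450 randomized. 1150 - 450 = 700, so the number not randomized lies between 0 and 700. How many of them took a run-in dose is not stated, and the upper bound includes screen failures who never did.

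**The case against.** The strongest reply has three parts.

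First, everyone takes placebo in the run-in. Tabulating it by later arm describes the randomized groups before treatment, and leaving out non-randomized subjects cannot bias centanafadine against placebo. This stands, and is a reason to keep the by-arm columns.

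Second, no protocol commitment is broken. Protocol 7.5 ties the Safety Sample to safety in the double-blind period and promises no run-in tables. This also stands, but by the same token nothing in the protocol required the SAP to carry that sample back into the run-in.

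Third, for rare events such as deaths and SAEs a listing is the informative output, and CT-9.1.2 and CT-9.2.2 lack the Safety Sample label that other listings carry (CT-8.7.3, CT-8.8.3, CT-10.3.1.1, CT-10.3.1.2). They may therefore cover everyone. This stands in part. The missing label does not settle the matter, because the matching double-blind listings CT-9.1.1 and CT-9.2.1 have none either and Section 9 states the Safety Sample as the general rule. Investigators must also report SAEs immediately (Protocol 5.3), so the gap lies in tabulation and not in capture.

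A reader might also infer more than the documents support:

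- *That CT-8.4.2 must show zero, or that all run-in deaths go unreported.* An adverse event that begins in the run-in and proves fatal after double-blind dosing could be counted there on one reading, although SAP 9.1.1 would also class it as a double-blind event. The listings may show the rest.
- *That the excluded subjects are mainly those who had problems.* Improvement of 30% or more on the ASRS and a positive drug screen also lead to early termination, and neither is an adverse event.
- *That the run-in carries particular risk because prior drugs have just been stopped.* Protocol Table 4.1-1 requires washouts of 7 to 28 days to be complete before the run-in begins, and subjects not receiving ADHD treatment are eligible.

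**Conclusion.** The point holds for the run-in incidence tables. As written, they cover only subjects who went on to randomization and a double-blind dose, and a death before that dose cannot appear in CT-8.4.2, apart from the deemed-exposed exception in SAP 5.1. Run-in deaths and SAEs may or may not appear in CT-9.1.2 and CT-9.2.2, because the analysis set is not stated. Run-in discontinuations for adverse events have no table or listing of their own.

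The size cannot be given. The documents state neither how many subjects took a run-in dose nor how many of those were not randomized, so any claim about how far event rates are understated would be unsupported. The conclusion rests on reading the Safety Sample definition and the table titles literally. It concerns completeness of run-in safety reporting, leaves the efficacy and double-blind safety comparisons untouched, and is minor.

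**What to change.** - In SAP Sections 9 and 9.1.2, and in the later run-in subsections, define the run-in safety population as Enrolled Sample subjects with at least one run-in placebo dose.
- Apply it to CT-8.1.2, 8.2.2, 8.4.2, 8.5.2.1, 10.3.x, 10.4.2, 10.5.2, 11.3.x, 12.4.x, 12.5.x, 14.2.x, 17.3 and 17.4. Show an overall column and a not-randomized column beside the existing by-arm columns.
- Add a summary or listing of run-in discontinuations due to adverse events.
- State that CT-9.1.2 and CT-9.2.2 cover the same set.

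The cost is a population flag, two added columns and one new output: slightly more programming, with no new data.

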9.2 Clinical Laboratory Tests

Summary statistics for routine clinical laboratory measurements will be provided. For The double-blind treatment period laboratory tests, change from baseline for the double-blind

SAP 405-201-00014

treatment period will be summarized by treatment group. Potentially clinically relevant results in laboratory tests will also be summarized.

9.2.1 Clinical Laboratory Tests in Double-Blind Treatment Period

Potentially clinically relevant laboratory measurement test results in the double-blind treatment period will be identified for the Safety Sample and will be summarized by treatment group and listed. Criteria for identifying laboratory values of potential clinical relevance are provided in [Appendix 2](#).

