13.	Subjects that have a positive alcohol test (via breathalyzer or blood), a positive drug screen for cocaine, or other illicit drugs (excluding marijuana). Subjects with a positive drug screen for confirmed prescription or OTC use of ADHD medications at screening will be required to undergo a washout period (Section 4). NOTE: Subjects that test positive for marijuana may be permitted to be enrolled if they have no evidence of a substance use disorder, and if they agree to refrain from use for the duration of the trial. Allowance for subjects testing positive for marijuana at screening require explicit approval from the medical monitor.
14.	Subjects with a known intellectual disability or clinical evidence of intellectual disability based on the opinion of the investigator.
15.	Subjects with insulin-dependent diabetes mellitus are excluded. Subjects with non-insulin-dependent diabetes mellitus may be eligible for the trial if their condition is stable as determined by satisfying ALL of the following criteria: 
 • Screening glucose (non-fasting) < 200 mg/dL. (If the non-fasting glucose is \geq 200 mg/dL, subjects must be retested in the fasting state. Fasting glucose must be \leq 125 mg/dL.), • Subject has been maintained on a stable regimen of oral anti-diabetic medication(s) for at least 28 days prior to screening or diabetes has been well-controlled by diet for at least 28 days prior to screening, • Subject has not had any hospitalizations within the 12 months prior to screening due to diabetes or complications related to diabetes, AND • Subject's diabetes is not newly diagnosed during screening for the trial.
16.	Subjects presenting with, or having a history of, uncontrolled hypertension (systolic blood pressure > 140 mmHg or diastolic blood pressure > 90 mmHg) or symptomatic hypotension, or orthostatic hypotension which is defined as a decrease of \geq 30 mmHg in systolic blood pressure or a decrease of \geq 20 mmHg in diastolic blood pressure after at least 3 minutes standing compared with the previous supine blood pressure, OR development of symptoms.
17.	Subjects with known ischemic heart disease or history of myocardial infarction, congestive heart failure (whether controlled or uncontrolled), angioplasty, stenting, coronary artery bypass surgery, or other serious cardiac problems that would place him/her at increased vulnerability to the sympathomimetic effects of a stimulant medication.

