9.4.1 ECG Data in the Double-Blind Treatment Period

Potentially clinically relevant changes in the 12-lead ECG identified in the double-blind treatment period for the Safety Sample will be listed and summarized by treatment group. Criteria for identifying ECG measurements of potential clinical relevance are provided in [Appendix 3](#).

Categorical changes in ECG parameters during the double-blind treatment period will be summarized based on the following criteria:

Categorical Change Criteria in QT/QTc Parameters		
Classification	Category	Criteria
QT	New Onset (> 450 Msec)	New onset (>450 msec) in QT means a subject who attains a value > 450 msec during treatment period but not at baseline.
QTc *	New Onset (> 450 Msec)	New onset (> 450 msec) in QTc means a subject who attains a value > 450 msec during treatment period but not at baseline.

SAP 405-201-00014

Categorical Change Criteria in QT/QTc Parameters		
Classification	Category	Criteria
	New Onset (> 450 Msec) And > 10% Increase	New onset (> 450 msec) and > 10% increase in QTc means a subject who attains a value > 450 msec and > 10% increase during treatment period but not at baseline
	New Onset (> 500 Msec)	New onset (> 500 msec) in QTc means a subject who attains a value > 500 msec during treatment period but not at baseline.
	Increase 30 - 60 Msec	Increase from baseline value > 30 and ≤ 60 msec in QTc
	Increase > 60 Msec	Increase from baseline value > 60 msec in QTc

* QTc categorical change criteria apply to QTcB, QTcF and QTcN.

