Appendix 1 Criteria for Identifying Vital Signs of Potential Clinical Relevance

Variable	Criterion Value ^a	Change Relative to Baseline ^a
Heart Rate ^b	> 100 bpm < 50 bpm	≥ 10 bpm increase ≥ 10 bpm decrease
Systolic Blood Pressure ^b	≥ 140 mmHg < 90 mmHg	≥ 20 mmHg increase ≥ 20 mmHg decrease
Diastolic Blood Pressure ^b	≥ 90 mmHg < 60 mmHg	≥ 10 mmHg increase ≥ 10 mmHg decrease
Orthostatic Hypotension	≥ 30 mmHg decrease in systolic blood pressure or a ≥ 20 mmHg in diastolic blood pressure after at least 3 minutes of standing compared to the previous supine blood pressure.	Not Applicable (baseline status not considered)
Orthostatic Tachycardia	≥ 25 bpm increase in heart rate from supine to standing	Not Applicable (baseline status not considered)
Weight	-	≥ 7% increase ≥ 7% decrease

^a In order to be identified as potentially clinically relevant, an on-treatment value must meet the “Criterion Value” and also represent a change from the subject’s baseline value of at least the magnitude shown in the “Change Relative to Baseline” column.

^b As defined in “Supplementary Suggestions for Preparing an Integrated Summary of Safety Information in an Original NDA Submission and for Organizing Information in Periodic Safety Updates,” FDA Division of Neuropharmacological Drug Products draft (2/27/87).

SAP 405-201-00014

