Appendix 2 Criteria for Identifying Laboratory Values of Potential Clinical Relevance

Laboratory Tests	Criteria
Chemistry	
AST (SGOT)	≥ 3 x upper limit of normal (ULN)
ALT (SGPT)	≥ 3 x ULN
Alkaline phosphatase	≥ 3 x ULN
BUN	≥ 30 mg/dL
Creatinine	≥ 2.0 mg/dL
Uric Acid	
Men	≥ 10.5 mg/dL
Women	≥ 8.5 mg/dL
Bilirubin (total)	≥ 2.0 mg/dL
Creatine Phosphokinase (CPK)	> 3 x ULN
Hematology	
Hematocrit	
Men	≤ 37 % and decrease of ≥ 3 percentage points from Baseline
Women	≤ 32 % and decrease of ≥ 3 percentage points from Baseline
Hemoglobin	
Men	≤ 11.5 g/dL
Women	≤ 9.5 g/dL
White blood count	≤ 2,800/ mm ³ or ≥ 16,000/ mm ³
Eosinophils	≥ 10%
Neutrophils	≤ 15%
Absolute neutrophil count	≤ 1,500/ mm ³
Platelet count	≤ 75,000/ mm ³ or ≥ 700,000/ mm ³
Urinalysis	
Protein	Increase of ≥ 2 units
Glucose	Increase of ≥ 2 units
Additional Criteria	
Chloride	≤ 90 mEq/L or ≥ 118 mEq/L
Potassium	≤ 2.5 mEq/L or ≥ 6.5 mEq/L
Sodium	≤ 126 mEq/L or ≥ 156 mEq/L
Calcium	≤ 8.2 mg/dL or ≥ 12 mg/dL
Glucose	
Fasting	≥ 100 mg/dL
Non-Fasting	≥ 200 mg/dL
Total Cholesterol, Fasting	≥ 240 mg/dL
LDL Cholesterol, Fasting	≥ 160 mg/dL
HDL Cholesterol, Fasting	
Men	< 40 mg/dL
Women	< 50 mg/dL
Triglycerides, Fasting	≥ 150 mg/dL

SAP 405-201-00014

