- CT-10.2.1.1 Listing of Laboratory Test Values with Potential Clinical Relevance During the Double-Blind Treatment Period by Subject (Safety Sample)
- CT-10.2.1.2 Listing of Laboratory Test Values with Potential Clinical Relevance During the Double-Blind Treatment Period by Test (Safety Sample)
- CT-10.2.2 Incidence of Laboratory Test Values with Potential Clinical Relevance During the Double-Blind Treatment Period (Safety Sample)
- CT-10.2.3.1 Mean Change from Baseline of the Double-Blind Treatment Period in Clinical Laboratory Test Results - Serum Chemistry (Safety Sample)
- CT-10.2.3.2 Mean Change from Baseline of the Double-Blind Treatment Period in Clinical Laboratory Test Results - Hematology (Safety Sample)
- CT-10.2.3.3 Mean Change from Baseline of the Double-Blind Treatment Period in Clinical Laboratory Test Results - Urinalysis (Safety Sample)
- CT-10.3.1.1 Listing of Laboratory Test Values with Potential Clinical Relevance During the Single-Blind Placebo Run-in Period by Subject (Safety Sample)
- CT-10.3.1.2 Listing of Laboratory Test Values with Potential Clinical Relevance During the Single-Blind Placebo Run-in Period by Test (Safety Sample)
- CT-10.3.2 Incidence of Laboratory Test Values with Potential Clinical Relevance During the Single-Blind Placebo Run-in Period (Safety Sample)
- CT-10.3.3.1 Mean Change from Baseline of the Single-Blind Placebo Run-in Period in Clinical Laboratory Test Results During the Single-Blind Placebo Run-in Period - Serum Chemistry (Safety Sample)
- CT-10.3.3.2 Mean Change from Baseline of the Single-Blind Placebo Run-in Period in Clinical Laboratory Test Results During the Single-Blind Placebo Run-in Period - Hematology (Safety Sample)

SAP 405-201-00014

CT-10.3.3.3 Mean Change from Baseline of the Single-Blind Placebo Run-in Period in Clinical Laboratory Test Results During the Single-Blind Placebo Run-in Period - Urinalysis (Safety Sample)

CT-10.4.1 Incidence of Potentially Liver Injury Related Laboratory Test Abnormalities During the Double-Blind Treatment Period (Safety Sample)

CT-10.4.2 Incidence of Potentially Liver Injury Related Laboratory Test Abnormalities During the Single-Blind Placebo Run-in Period (Safety Sample)

CT-10.5.1 Listing of Potentially Liver Injury Related Laboratory Test Abnormalities During the Double-Blind Treatment Period (Safety Sample)

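### As written, the laboratory incidence table CT-10.2.2 mixes pre-existing with new abnormalities, because 23 of the 26 criteria carry no baseline condition; this dilutes the contrast between arms without biasing it

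*SAP*

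**What the plan says.** SAP 9.2.1 says that "Potentially clinically relevant laboratory measurement test results in the double-blind treatment period will be identified for the Safety Sample", to be summarized by treatment group and listed. It then points to the appendix: "Criteria for identifying laboratory values of potential clinical relevance are provided in" Appendix 2, which repeats Protocol Appendix 2. The section sets no condition on baseline status and no restriction on the denominator. The output is CT-10.2.2 in SAP Section 13, titled "Incidence of Laboratory Test Values with Potential Clinical Relevance During the Double-Blind Treatment Period (Safety Sample"). The table list contains no laboratory shift table and no new-onset laboratory table.

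Within Appendix 2, three tests refer to a change. Hematocrit does (for men, "≤ 37 % and decrease of ≥ 3 percentage points from Baseline"), and so do urine protein and urine glucose ("Increase of ≥ 2 units"). The remaining entries are absolute cut-offs.

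Other safety domains in the SAP mostly do account for baseline:
- Vital signs (Appendix 1) and ECG (Appendix 3) share a footnote, "In order to be identified as potentially clinically relevant, an on-treatment value must meet the" criterion value and also show a minimum change from baseline. This applies to most of their parameters.
- The new-onset QT and QTc categories in SAP 9.4.1 require the value to occur "during treatment period but not at baseline".
- The TEAE definition (SAP 9.1.1) and the C-SSRS emergence definitions (SAP 9.6) also separate new from existing.

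**The concern.** A subject who enters with a value beyond an Appendix 2 cut-off and simply stays there would be counted in CT-10.2.2 alongside a subject whose value became abnormal on drug. If many subjects qualify at entry, the tabulated rates in all arms sit on a shared background. A real drug effect then appears as a smaller ratio, and the absolute rate cannot be read as the rate of new abnormalities. No other listed table gives a between-arm rate of new laboratory abnormalities.

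**Working it through.** **Step 1. Count the criteria.** SAP Appendix 2 lists 8 chemistry, 7 hematology, 2 urinalysis and 9 additional tests: 8 + 7 + 2 + 9 = 26. Three carry a change from baseline (hematocrit, urine protein, urine glucose), so 26 − 3 = 23 do not.

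**Step 2. Compare those 23 with the entry limits** (Protocol Table 3.4.3-1, exclusions 15 and 18).

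| Test | Excluded at entry | Flagged on treatment | Can qualify at entry? |
|---|---|---|---|
| AST, ALT | > 2 × ULN | ≥ 3 × ULN | No |
| Creatinine | ≥ 2 mg/dL | ≥ 2.0 mg/dL | No |
| Platelets | ≤ 75,000/mm³ | ≤ 75,000 or ≥ 700,000/mm³ | High side only |
| Neutrophils, absolute | ≤ 1000/mm³ | ≤ 1,500/mm³ | Yes, above 1000 to 1500 |
| Hemoglobin | ≤ 9 g/dL | ≤ 11.5 (men), ≤ 9.5 (women) g/dL | Yes, above 9 to 11.5 or 9.5 |
| Glucose, fasting | > 125 mg/dL on retest, in non-insulin-dependent diabetes | ≥ 100 mg/dL | Yes, 100 to 125 |
| Lipids (4 tests) | No numeric limit | Appendix 2 cut-offs | Yes |

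For glucose, exclusion 15 says "Subjects with non-insulin-dependent diabetes mellitus may be eligible for the trial if their condition is stable", and the fasting retest applies when the nonfasting value is 200 mg/dL or more. Exclusion 18 adds HbA1c of 7% or more for everyone, which narrows this group but does not close the 100 to 125 band. Uric acid, CPK, eosinophils, bilirubin and electrolytes also have no numeric entry limit.

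Three tests (AST, ALT, creatinine) are fully closed at screening, so 23 − 3 = 20 can be met at entry, counting platelets for the high side.

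**Step 3. Illustrate the dilution.** The documents give neither a baseline prevalence nor an event rate, so every input here is an assumption. Let b be the share already qualifying at baseline, r the share of those who qualify again on treatment (taken as equal in the arms), and p the new-onset risk among the rest.

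Tabulated rate = b·r + (1 − b)·p

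With p = 10% on drug and 5% on placebo, the true ratio is 2.0 and the difference 5.0 points. With full persistence (r = 1):

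| b | Drug | Placebo | Ratio | Difference |
|---|---|---|---|---|
| 10% | 0.10 + 0.90 × 0.10 = 19.0% | 0.10 + 0.90 × 0.05 = 14.5% | 1.31 | 4.5 points |
| 20% | 0.20 + 0.80 × 0.10 = 28.0% | 0.20 + 0.80 × 0.05 = 24.0% | 1.17 | 4.0 points |
| 30% | 0.30 + 0.70 × 0.10 = 37.0% | 0.30 + 0.70 × 0.05 = 33.5% | 1.10 | 3.5 points |

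Full persistence is the worst case for the ratio. At r = 0.6 and b = 10% the rates are 0.06 + 0.09 = 15.0% and 0.06 + 0.045 = 10.5%, a ratio of 1.43 instead of 1.31. The difference equals (1 − b) × 5 points whatever r is, so persistence does not affect it.

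A second assumed case, 8% against 3%, has a true ratio of 2.67. It falls to between 1.52 and 1.07 as b runs from 10% to 40% and r from 0.6 to 1.0.

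**The case against.** - **The rule is read from silence.** Neither SAP 9.2.1 nor Appendix 2 says that baseline status is ignored, and Section 13 gives table titles without shells or footnotes. Where the SAP means to ignore baseline it says so, as for the orthostatic criteria in Appendix 1. A reader might infer that the plan expressly directs pre-existing cases to be counted; it does not. What stands is that, applied literally, the text counts them, and nothing in the plan would stop a programmer doing so.
- **CT-10.2.2 is not the only laboratory comparison.** SAP 9.2 specifies change from baseline by arm (CT-10.2.3.1 to 10.2.3.3). Run-in values of potential relevance are tabulated by treatment group (CT-10.3.2), listings exist by subject and by test, and liver injury has its own table. Values that the investigator considers medically relevant become adverse events (Protocol 5.1) and reach the TEAE tables. A reader might infer that laboratory effects would be hidden or uninterpretable; these outputs make that too strong. None of them, however, supplies a rate of new abnormalities by arm.
- **Entry is not unrestricted.** Exclusion 18 also removes subjects with other abnormalities judged medically significant, and Protocol 3.7.5.2 requires medical monitor permission to enrol after a clinically significant screening result. Both are judgements not tied to the Appendix 2 cut-offs, so they reduce the overlap by an unknown amount.
- **Replacing the count would lose information.** If baseline-abnormal subjects were removed, someone moving from neutrophils of 1,400 to 600 would disappear from the incidence table. This objection stands, and the fix allows for it.

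**Conclusion.** The point holds as a limited one. For 23 of 26 tests the flag has no baseline condition, and 20 of those can be met at entry on the numeric limits, subject to clinical judgement. AST, ALT, creatinine and low platelets are screened out, although a value can still move between screening and baseline. CT-10.2.2 as written therefore mixes pre-existing with new abnormalities.

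A reader might take this as bias in favour of the drug. The documents do not support that: pre-existing cases are balanced in expectation by randomization, so the effect is dilution and an absolute rate that is not an incidence of new events. On the stated assumptions the ratio falls from 2.0 to 1.31 to 1.10 and the difference from 5.0 to 4.5 to 3.5 points. The actual size is unknown and will differ by test; one prevalence range cannot describe both neutrophils and lipids. The table is descriptive, so no hypothesis test or alpha allocation depends on it. The case for change is that it is cheap and supplies a comparison the plan otherwise lacks.

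**What to change.** In SAP 9.2.1 and CT-10.2.2:
1. Keep the existing all-subject count and the unrestricted listings.
2. Add a treatment-emergent count: criterion met on treatment and not met at the double-blind baseline, which SAP 7.1 already defines. Use subjects not meeting the criterion at that baseline as the denominator for each test.
3. Add a shift table, or a worsening rule, so that subjects who deteriorate from an abnormal baseline stay visible.
4. State how a nonfasting baseline is handled for the fasting glucose and lipid criteria. Protocol 3.7.5.2 allows nonfasting samples at screening and asks for fasting only if possible at most visits, but requires a fast at Day 42/ET, so the baseline and on-treatment values may not be comparable.

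The cost is SAP wording, a baseline filter, denominators that vary by test, and one more table.
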